# **Synopsis**

Study Title:	A randomized controlled clinical trial to investigate the capability of Straumann® VivOss™ compared to Geistlich Bio-Oss® in sinus floor augmentation.					
Protocol Code:	CR 03/13					
Objective	To demonstrate superiority of Straumann ® VivOss ™ compared to Geistlich Bio-Oss ® in regards to the ratio of newly formed bone to residual bone substitute.					
Study Design:	A prospective, randomized, controlled, open label study.					
	Inclusion Criteria					
	Subject must have voluntarily signed the informed consent before any study related action					
	Males and females with at least 18 years of age (including 18 years)					
	

Subject needs augmentation procedure in the sinus to prepare for implant placement.

					
	4. Subject must have a residual bone height of 2 to 4 mm.					
	
 
Adequate oral hygiene ((Full mouth plaque index (O'Leary, et al. 1972) <25%) at baseline
 
					
	6. Adequate control of inflammation ((full mouth bleeding on probing (Ainamo and Bay 1975)) ≤25% at baseline					
	Exclusion Criteria					
Subject Deputation:	Pre-surgical exclusion criteria					
Subject Population:	Systemic disease that would interfere with bone or wound healing and dental implant therapy (e.g. uncontrolled diabetes)					
	Any contraindications for general bone grafting and oral surgical procedures					
	
 
Any anomalies of the sinus that could interfere with planned procedures
 
					
	4. History of local irradiation therapy					
	5. Local inflammation, including untreated periodontitis					
	Medical conditions requiring chronic high dose steroid therapy					
	7. Treatment with an investigational drug or device within a 30 day period immediately prior to surgery at visit 2, or expected participation in any other investigational drug or device study during the conduct of this trial.					

Version 6.0 Page 4 of 47

	Antibiotic treatment or anti-inflammatory treatment within 4     weeks prior to surgery
	History of alcoholism or drug abuse
	10. Immunocompromised subjects
	11. Subjects who smoke >10 cigarettes per day or tobacco equivalents or chew tobacco
	12. Conditions or circumstances, in the opinion of the investigator, which would prevent completion of study participation or interfere with analysis of study results, such as history of non-compliance or unreliability
	
 
Physical or mental disabilities that would interfere with the ability to perform adequate oral hygiene
 

	
 
Current pregnancy (pregnancy test) and breastfeeding women
 

	Secondary exclusion criteria at or after surgery
	Defects of the Schneider Membrane
Treatment Plan:	
 
Visit 0 (Informed Consent, 2 to 14 days before screening):         signing informed consent after informed consent process.
 
Visit 1 (Screening):         pregnancy test (only if female with childbearing potential),         demographic data, medical/dental history, inclusion/exclusion         criteria, planned implant site, CBCT (not older than 12 months)
 
Visit 2 (Sinus elevation):         adverse events, concomitant medication, randomization, details         of surgery, secondary exclusion criteria, intra-oral photographs
 
Visit 3 (wound healing assessment):         adverse events, concomitant medication, suture removal, post-         operative wound healing control, intra-oral photographs
 
Visit 4 (Implant placement / Histology):         adverse events, concomitant medication, histology sampling,         dental implant placement, intra-oral photographs
 
Visit 5 (wound healing assessment):         adverse events, concomitant medication, suture removal, post-         operative wound healing control, intra-oral photographs
 
Visit 6 (Initial implant loading):         adverse events, concomitant medication, survival of the dental         implant, success of the dental implant, intra-oral photographs,         periapical x-ray
 

Primary Endpoint:	The histological evaluation of the ratio of newly formed bone to residual bone graft in Straumann ® VivOss ™ compared to Geistlich BioOss ® at visit 4 (6 month ± 7 days, after sinus elevation).
Secondary Endpoints:	
 
Survival rate of study implants evaluated at visit 6 (Initial implant loading)
 
Success rate of study implants evaluated at visit 6 (Initial implant loading)
 

Version 6.0 Page 5 of 47

Study Device(s):	Test: Synthetic biphasic calcium phosphate (HA/TCP 10:90)  Straumann® VivOss™  Comparator: Demineralized bovine bone mineral (Geistlich Bio-Oss®)
Safety:	The subjects will be monitored continuously for adverse events by the investigators.
Registration Status:	All products are CE marked
Study Duration:	The total study duration for each subject should be 9-14 months from screening to last visit.
Number of participating Centres:	Two centres
Number of subjects planned to be enrolled:	50 subjects (25 in the test group, 25 in the comparator group)
Sponsor:	Institut Straumann AG [name] [name] Switzerland
Investigators:	[name], Zurich (Switzerland) [name]. [name], Constance (Germany)
Compliance:	This study and any amendments will be performed according to ISO 14155 (Second Edition, 2011-02-01) and conform to the Declaration of Helsinki (last revised Seoul 2008) and local legal and regulatory requirements.

Version 6.0 Page 6 of 47

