### **Schedule of Assessment**

	Visit 0	Visit 1	Visit 2	Visit 3	Visit 4	Visit 5	Visit 6
Tasks	Informed Consent	Screening Visit	Sinus elevation (Baseline)	Wound healing assessment	Implant placement	Wound healing assessment	Initial implant loading
	28-2 days before screening	14-0 days before Baseline	Day 0	Day 7-14	6 months ± 7 days	7-14 days after visit 4	4 months ± 1 month after visit 4
Informed Consent	Х						
If female, pregnancy test		Х					
Demographics (date of birth, gender, ethnic origin)		х					
Medical & Dental History		Х					
Inclusion /Exclusion Criteria		Х					
Planned implant site		Х					
Cone Beam CT (CBCT)		X *1, *2					
Adverse events			Х	Х	Х	Х	Х
Concomitant medication		Х	Х	X	Х	X	Х
Randomization			Х				
Augmentation			Х				
Secondary inclusion criteria			Х				
Intra-oral Photographs			Х	X	Х	X	X
Suture Removal				X		X	
Implant Placement					Х		
Bone Biopsy					Х		
Wound healing assessment				X		X	
Periapical x-ray							X *2
Implant survival							X
Implant success							Х

\*1 If an CBCT was taken up to 12 months in advance to the baseline visit (visit 2) there is no need to take a new CBCT.

Version 6.0 Page 7 of 47

\*2 Radiographs should only be taken if clinically necessary.

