### 4.3 Study Treatments

Before entering into the study, each subject has to sign an informed consent. A subject is enrolled if she/he meets all inclusion criteria and at the same time does not meet any exclusion criteria. Enrolled subjects will be scheduled for sinus elevation. At surgery subject eligibility will again be evaluated according to secondary exclusion criteria. Subjects who do not meet any secondary exclusion criteria are randomized to one of the following groups:

- a) Sinus floor elevation with Straumann® VivOss™
- b) Sinus floor elevation with Geistlich Bio-Oss®

After a healing time of 1-2 weeks, sutures are removed, and the wound healing is evaluated. After a healing time of 6 months, an intermediate osteotomy for the dental implant placement is done by means of a trephine burr in such a way that the biopsy is harvested at the same time. Dental implant placement will be completed according to the standard procedure of the clinic. After a healing time of 1-2 weeks, the sutures are removed and the wound healing is evaluated. 4 months after implant placement the implant is initially loaded and the survival as well as the success rate will be evaluated.

Version 6.0 Page 14 of 47

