#### 7.9 Randomization

Subjects will be randomized either to the test group receiving Straumann® VivOss™ or comparator group receiving Geistlich Bio-Oss®. The master randomization list will be kept in a secure repository in the office of the Sponsor. The study centers have to contact the Sponsor by email or phone to request randomization of a subject, the Sponsor will send a randomization form including randomization details via email or fax. Although this study is not blinded, no access to the randomization list will be available to the study centre, the external Monitors, the subjects and the Straumann non-Clinical-Research project team.

Site/s of Biopsy

The site of biopsy in each sinus depends on the number of implants to be placed in the sinus. If more than one implant will be placed the most preferred site will be position 6, followed by position 5, followed by position 7, the least preferred position is position 4.

Version 6.0 Page 20 of 47

If more than one implant is placed, the investigator should take 2 biopsies following the preference list above. The second biopsy should be taken as backup in case the first biopsy cannot be evaluated.

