#### 10.4.4 Not Treated (NT)

Subjects enrolled in the study who did not receive the study device will be excluded from the analysis.

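### The synopsis leaves room to exclude a subject for a membrane defect after the allocation is known, whereas section 4.3 makes that check before randomisation

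*Combined protocol and SAP*

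**What the plan says.** There is one secondary exclusion criterion, "Defects of the Schneider Membrane". Its timing is described differently in different places.

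- **Synopsis, exclusion criteria:** the heading is "Secondary exclusion criteria at or after surgery".
- **Section 4.3:** eligibility is re-checked at surgery, and "Subjects who do not meet any secondary exclusion criteria are randomized to one of the following groups".
- **Section 5.3:** the exclusion is tied to sinus floor elevation. Nothing is said about later discovery or about the order relative to randomisation.
- **Synopsis, visit 2 list:** "concomitant medication, randomization, details" comes first, then "of surgery, secondary exclusion criteria".
- **Schedule of Assessment:** the rows run randomisation, augmentation, then "Secondary inclusion criteria". Section 7.11 carries the same inclusion label but points to 5.3, which is an exclusion criterion.
- **Section 7.9:** the centre contacts the sponsor by email or phone, and "the Sponsor will send a randomization form including randomization details via email or fax". No time relative to the membrane check is given.

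On analysis, section 10.2 bases the superiority test on the per-protocol set. Section 8.4 replaces anyone who leaves that set while recruitment is open. Section 10.4.4 adds: "Subjects enrolled in the study who did not receive the study device will be excluded from the analysis".

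**The concern.** The graft is placed at visit 2 and the study is not blinded, so from that surgery onward the surgeon knows the arm. An exclusion made after surgery is therefore made with knowledge of the allocation. Whether a membrane finding counts as a defect is a judgement, and the same person may have an impression of how the site will heal. If that judgement were applied differently in the two arms, the arms analysed would no longer be the arms randomised. The primary test is on the per-protocol set and leavers are replaced, so such a removal could pass into the main result without showing as missing data.

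**Working it through.** **1. The plan's own figure.** Section 10.3 gives a difference of 0.4, SD 0.5, two-sided 5% and 80% power.

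n per group = 2 × [SD × (z₀.₉₇₅ + z₀.₈₀) / Δ]² = 2 × [0.5 × (1.960 + 0.8416) / 0.4]² = 2 × 3.502² = 24.53, rounded up to 25.

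The stated 25 reproduces. This is the normal approximation; exact t power at 25 per group is 79.2%.

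**2. Timing, side by side.**

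| Place | When the check is made | Order relative to randomisation |
|---|---|---|
| Synopsis heading | during surgery or later | not stated; later means after allocation |
| 4.3 | at surgery | check first |
| 5.3 | at sinus floor elevation | not stated |
| 7.9 | not mentioned | time of request not stated |

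The synopsis and 4.3 cannot both be followed for a defect identified after surgery. No passage limits the synopsis wording to the time before randomisation.

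**3. What happens to a subject with a defect.**

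| Case | Per protocol (10.4.1) | Full analysis (10.4.2) | Safety (10.4.3) |
|---|---|---|---|
| A. 4.3 followed, defect found at the check | never randomised; screening failure under 8.2 | – | – |
| B. Randomised, grafted, then excluded | out if excluded before finishing the study | in, if any post-randomisation measurement exists | in |
| C. Randomised, defect found, never grafted | out in practice: no study graft, and 10.4.4 applies | out | out |

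Case B is the one the synopsis wording opens. Case C needs the allocation to be obtained before the check, which 7.9 neither requires nor rules out. A case C subject has been randomised and so does not fit the screening-failure definition in 8.2. In case B, membership of the full analysis set does not by itself supply a primary outcome: the ratio comes from the visit 4 biopsy at 6 months, and a subject already taken out of the study may have none.

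**4. Size.** The documents give no defect or exclusion rate, so these are assumed scenarios. Suppose k of n subjects in one arm have ratios lower than the rest of that arm by d, and are excluded:

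shift in the difference = (k / n) × d = (2 / 25) × 0.5 = 0.04, and 0.04 / 0.4 = 10% of the planned effect.

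If the two are replaced by subjects like the remaining 23, the arm mean stays at the mean of those 23. The shift is still 0.04, although n is back to 25.

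A simulation with no true difference (SD 0.5, 25 per arm, 20,000 trials per setting) excluded subjects from one arm only, on an impression correlated with the outcome, without replacement:

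| Excluded | Correlation | Bias | Two-sided type I error |
|---|---|---|---|
| 2 of 25 | 0 | −0.001 | 5.0% |
| 2 of 25 | 0.3 to 0.5 | 0.022 to 0.038 | 5.4% to 5.8% |
| 5 of 25 | 0 | 0.001 | 4.9% |
| 5 of 25 | 0.3 to 0.5 | 0.049 to 0.083 | 6.4% to 8.8% |

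Exclusions unrelated to outcome do no harm to validity; the harm comes from selection.

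**The case against.** The strongest reply is that the body of the protocol already has the safe order. Section 4.3 checks and then randomises, 5.3 says nothing about exclusion after surgery, and 8.2 makes a subject who fails the check a screening failure. On that reading the synopsis heading is loose wording. This stands to the extent that post-allocation exclusion is permitted by one passage and not planned by the protocol as a whole. It does not remove the contradiction, since nothing says which text governs.

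Stronger readings are tempting, and the documents do not support them:

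- *A reader might infer from the visit 2 list and the schedule that randomisation and grafting precede the check.* The schedule is not chronological: implant placement is listed above bone biopsy, although 4.3 and 7.15 take the biopsy first. Row order is weak evidence.
- *A reader might infer that email or fax delivery forces sites to obtain the allocation before surgery.* Section 7.9 sets no time and allows the request by phone. Early disclosure is possible, but no passage says that it occurs.
- *A reader might infer that excluded subjects vanish from every analysis set.* That is true only of case C. Grafted subjects stay in the safety set and, with post-randomisation data, in the full analysis set.
- *A reader might infer a loss of power.* Assumed unreplaced exclusions of 10%, 20% or 30% would leave 22.5, 20 or 17.5 per arm, with exact t power of 74.6%, 69.3% or 63.2% against 79.2%. But the rates are assumptions, and section 8.4 provides replacement while recruitment is open.

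Section 7.12 also requires photographs of the open and the filled sinus at visit 2. They are a partial record of what was seen, but the plan assigns no independent reading of them.

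**Conclusion.** The point holds as a contradiction that leaves a route to selection bias open. If the synopsis is followed, a surgeon who knows the arm can exclude a subject, who then leaves the per-protocol primary analysis and may be replaced. If 4.3 is followed, no exclusion follows allocation. The documents do not show that such exclusions are intended.

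The size cannot be determined. The shift of about 0.04 assumes 2 of 25 exclusions confined to one arm, with ratios 0.5 lower; in the comparable simulated settings the type I error rises only to 5.4–5.8%. The effect is modest unless exclusions are several and one-sided. It deserves correction because the primary test is per protocol, replacement would conceal the loss, and the repair is cheap.

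**What to change.** 1. Reconcile the synopsis heading, the synopsis visit 2 list and the schedule row with the check-then-randomise order of 4.3 and the timing in 5.3. Correct the inclusion label in the schedule and in 7.11, since the criterion is an exclusion.
2. State in 7.9 that the allocation is requested or disclosed only after the result of the membrane check has been recorded.
3. State in section 10.4 that a defect found after allocation is recorded but does not by itself remove the subject from the analysis.
4. Report the primary comparison also on all randomised subjects who have a biopsy ratio, and list by arm any subjects randomised but not grafted. They have no ratio to analyse, so placing them in the full analysis set would not be enough. Nor would the full analysis set alone alter a primary test based on the per-protocol set.

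The cost is a few lines of text, one supplementary analysis, and a small logistic step during surgery while the allocation is released. How a membrane defect is handled clinically remains for the sponsor to settle.

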### **Schedule of Assessment**

	Visit 0	Visit 1	Visit 2	Visit 3	Visit 4	Visit 5	Visit 6
Tasks	Informed Consent	Screening Visit	Sinus elevation (Baseline)	Wound healing assessment	Implant placement	Wound healing assessment	Initial implant loading
	28-2 days before screening	14-0 days before Baseline	Day 0	Day 7-14	6 months ± 7 days	7-14 days after visit 4	4 months ± 1 month after visit 4
Informed Consent	Х						
If female, pregnancy test		Х					
Demographics (date of birth, gender, ethnic origin)		х					
Medical & Dental History		Х					
Inclusion /Exclusion Criteria		Х					
Planned implant site		Х					
Cone Beam CT (CBCT)		X *1, *2					
Adverse events			Х	Х	Х	Х	Х
Concomitant medication		Х	Х	X	Х	X	Х
Randomization			Х				
Augmentation			Х				
Secondary inclusion criteria			Х				
Intra-oral Photographs			Х	X	Х	X	X
Suture Removal				X		X	
Implant Placement					Х		
Bone Biopsy					Х		
Wound healing assessment				X		X	
Periapical x-ray							X *2
Implant survival							X
Implant success							Х

\*1 If an CBCT was taken up to 12 months in advance to the baseline visit (visit 2) there is no need to take a new CBCT.

Version 6.0 Page 7 of 47

\*2 Radiographs should only be taken if clinically necessary.

### **Abbreviations:**

ØDiameterAEAdverse EventBoPBleeding on Probing

CBCT Cone Beam Computed Tomography

CE Communauté Européenne (Marking of registered device in

Europe)

CRF Case Report Form

FDI Fédération Dentaire Internationale FMPPD Full Mouth Probing Pocket Depth

FU Follow-up

GBR Guided Bone Regeneration
GCP Good Clinical Practice

HA Hydroxyapatite IA Interim Analysis

ICF Informed Consent Form

ID Identity

IEC Independent Ethics Committee

ISO International Organization for Standardization

 $\begin{array}{ccc} mm & & & & \\ \mu m & & & \\ N & & & \\ PP & & & \\ Per & & \\ Protocol & \\ \end{array}$ 

SADE Serious Adverse Device Effect

SAE Serious Adverse Event

SD Study Day

STL Soft Tissue Level

TCP Tri-Calcium-Phosphate

USADE Unanticipated Serious Adverse Device Effect

Version 6.0 Page 8 of 47

### 2 Background and Rationale

Maxillary sinus floor elevation to allow the placement of endosseous implants has become a standard surgical procedure in the last decades with reliable long-term results, both in clinical  and experimental studies. 

Bone grafting procedures have been shown to be predictable methods for augmenting the bone volume in areas with deficient bone quantity or quality in order to allow dental implant insertion according to planned prosthetic position.

Autogenous bone grafts (autografts) have been recommended to be used in order to act as an osteoinductive and osteoconductive scaffold. The material is harvested at intraoral or extraoral sites. The successful use of autogenous bone as bone void filler has made this material the standard as it has already been for bone reconstructive surgery in orthopedics. Nevertheless, this material has a number of disadvantages. Most importantly, the necessity for a second site to harvest the autogenous bone increases the duration of the surgical intervention, the surgical risk as well as post-surgical morbidity at harvesting site. In order to avoid the drawbacks of this material, bone graft substitutes have been proposed. These can be classified in the following groups: allografts (from same species (human), but different individual), xenografts (from different species, usually animal derived from bovine origin) and alloplast (synthetic origin). They have been shown to be effective and have demonstrated a high implant success rate, but much controversy still exists regarding the capability of these materials to be resorbed and substituted by newly formed bone to allow adequate osseointegration of dental implants.

Bio-Oss®, a deproteinized bovine bone mineral, is one of the most commonly used and evidence-based bone substitute materials in the field of dental surgery.  Pre-clinical  and clinical studies  have shown that Bio-Oss® can preserve bone dimensions adequately. The combination of Bio-Oss® and the resorbable collagen membrane Bio-Gide® has been found to be effective for bone regeneration in situations where dental implants are placed. , 

Studies have shown that the biphasic calcium phosphate (BCP) Straumann BoneCeramic® used for sinus floor elevations or alveolar ridge preservation can result similar bone changes to standard graft material (Bio-Oss®), 16,17 and can result in excellent survival and success rates of dental implants placed subsequently. Straumann BoneCeramic® consists of hydroxyapatite (HA) and β-tricalcium phosphate (β-TCP) in a 60:40 ratio, so that the HA acts as a scaffold for space maintenance while the β-TCP resorbs and supports bone regeneration. A new second generation macro- and microporous BCP (mean micropore diameter 1 µm) has been developed with an HA/TCP ratio of 10:90 and controlled microporosity, which may be an important factor in the osteoconductive capacity of calcium phosphate ceramics. 19 This material has demonstrated biocompatibility and osteoconductivity and is designed to act as a scaffold that allows cells to infiltrate the site of the defect for subsequent bone regeneration and is designed to provide substitute degradation, i.e. chemical/non-cellular dissolution of BCP in parallel with resorption by osteoclasts. Bone formation starts with an organic cellular matrix being formed by cells (including pre-osteoblasts) around the BCP particles. Preclinical data have indicated that in addition to direct bone deposition on the surface of the BCP particles, mineralization and ossification also occurs in the inter-granular spaces. This occurs as a result of calcium and phosphate, released by substitute degradation, that become embedded in the organic matrix,

Version 6.0 Page 13 of 47

similar to the process of ossification that occurs during osteogenesis; this is assumed to enable random bone formation throughout the defect.

### 3 Study Endpoints

### 3.1 Primary Endpoint

• To histologically evaluate the ratio of newly formed bone to residual bone graft in Straumann® VivOss™ compared to Geistlich Bio-Oss® at 6 months (± 1 7 days) after sinus floor augmentation.

